 - d. Proportion of enrolled patients who complete the study and follow up evaluations. We aim to show that 70% of those assigned to MBSR will complete at least 6/8 intervention sessions. Additionally, assuming a 10% loss to follow up at each follow up time point we expect to have 65% who have completed all follow up evaluations.
 - e. Time to first follow up PCP or mental health professional visit.
2. The presence of MACE at 45 days as defined by the following diagnostic criteria:
 - a. Any death of an enrolled patient within 45 days of index ED visit.
 - b. Acute myocardial infarction and coronary revascularization as defined in the Third Universal Definition of Myocardial Infarction.[56]
 - c. Electronic medical record (EMR) review to assess intervening significant cardiopulmonary related diagnoses at 45 days.

Specific Aim 2: To determine the effect of an MBSR training program for patients with LRCP-A on mental health (longitudinal GAD-7 scores, quality of life (PROMIS Global Short Form), and ED resource utilization (return ED visits).

Forty subjects who screen positive for LRCP-A using the process outlined above will be assigned to one of two treatment arms. Enrolled subjects will be referred for standard primary care and/or psychiatric referral for therapy using IU Health's existing consult and referral infrastructure (Arm 1) or for therapy sessions using MBSR (Arm 2) [28, 31]. We plan to recruit eligible subjects for assignment in the 40 days prior to the start of each 8-week MBSR class series.

1. **Arm 1: Standard psychiatric referral:** Subjects will be referred for primary care provider (PCP) follow up and/or to psychiatry for further management and treatment of elevated anxiety levels according to standard of care. The treating ED provider will have discretion as to which referral option they believe to be more appropriate for each patient. This will occur using the hospital system's current infrastructure and act as a "time from referral to treatment" control. Thus, we will have a baseline for the average time it would take for an individual referred for evaluation or treatment to be seen. Subjects will receive a standard set of discharge instructions which will discuss anxiety, chest pain, and instructions for follow up with their PCP. For those patients without a PCP, we will provide a list of PCPs with whom they could establish care. Patients will also be given a resource list of mental health professionals with whom they

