could also schedule follow up with if directed by the ED provider. This list will be a custom list provided by our social work colleagues based upon individual patient factors (proximity to residence, insurance status, etc.) which is currently standard practice. We plan to also send a letter or EMR communication to the patient's PCP if they have one alerting them to their participation in the study, their study assignment, and encouraging further evaluation and management of their anxiety symptoms. For those without a PCP at time of enrollment we will query the patient at each follow up time-point for the establishment of primary care and send this letter if they have been able to do so at that time.

2. **Arm 2: MBSR intervention:** In addition to the standard referrals and discharge instructions discussed above, subjects assigned to MBSR will be offered a referral to a local MBSR course. The standard MBSR course meets one day per week for 8 weeks, with sessions being 2.5 hours in duration. A full day retreat (7 hours in length) is offered on a Saturday between sessions 6 and 7. The primary techniques are the "body scan", a noncritical assessment of bodily sensations when directing attention in a deliberate manner from the feet through the head and focused meditation with a special attention to breathing [57]. The full training program is presented in the intervention instruction manual and Table 1 outlines the contents of each weekly session. Our study interventionist will provide several options for the MBSR course (e.g., different days of the week and times of day) from which to choose to maximize convenience. To maximize MBSR availability for this pilot, these blocks will include groups open to non-study participants as well as closed dedicated study groups.

Table 1. Description of Mindfulness-Based Stress Reduction Sessions

Session #	Session Themes	Meditation Exercises	Didactic Teaching	Home Practice

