8	The rest of your life: Making the practice your own	
 ▪ Body scan ▪ MM ▪ Sitting meditation 	
 ▪ Review of the course with an emphasis on daily strategies for maintaining and deepening mindfulness skills ▪ Sharing of participant perspectives on the program; welcoming all comments 	
 ▪ Mindfulness resources handout ▪ Continuing the practice & making it your own ▪ Bringing seamless attention to life

Outcome assessments: The schedule of assessments is shown in Table 2. These assessments will take place in the method most convenient for the patient (telephone, mail, or online REDCap survey completion). These are all methods the PI and his research team are currently using. **The primary outcome of interest will be the mean longitudinal change in GAD-7 scores between intervention groups at each time point.**

Domain	Measure	# of Items	Time Period Investigated				
			ED	45 day	3 mo	6mo	12mo
MACE [†] Risk	HEART Score	5	x				
ACS Risk	PreTest Consult ACS	8	x				
Demographics	Age, Race, Gender, Education etc.	10	x				
Medication Use	Standard Items	2	x	x	x	x	x
Medical Comorbidity	9-Condition Checklist	9	x				
Chest Pain Symptoms	Custom Items and Numeric Rating Scale	5	x				
Somatization	Patient Health Questionnaire (PHQ-15)	15	x	x	x	x	x
Anxiety Severity	Generalized Anxiety Disorder Scale (GAD-7)	7	x	x	x	x	x
Panic	PHQ Panic Scale	5	x	x	x	x	x
Social Anxiety	Mini-SPIN	3	x	x	x	x	x
PTSD	4-Item screen	4	x	x	x	x	x
Depression	Patient Health Questionnaire (PHQ-8)	8	x	x	x	x	x
Cardiac Anxiety	Cardiac Anxiety Questionnaire	18	x	x	x	x	x
Resilience	Brief Resilience Scale	6	x				
Pain Catastrophizing	Pain Catastrophizing Scale	13	x				
Healthcare Utilization (12 mo Pre-ED)	Custom Items	6	x				
Healthcare Utilization (Post-ED assessment)	Custom Items	6		x	x	x	x
Healthcare Related Quality of Life	PROMIS Global Short Form	10	x	x	x	x	x
Life Trauma	Traumatic Life Events Questionnaire	18	x				
MBSR Mechanism of Action	Cognitive and Affective Mindfulness Scale-Revised (CAMS-R)	10	x	x	x	x	x
MBSR Evaluation	Toronto Mindfulness Scale (TMS)	13	x	x	x	x	x

[†]Major Adverse Cardiac Event

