The goals are to collect preliminary data regarding the feasibility and effectiveness of the MBSR referral and approach compared with standard of care referral. Eligibility, recruitment, and retention information will be tabulated. Frequencies and percentages will be summarized by group for categorical variables, and continuous and count variables will be summarized by group using the mean, standard deviation, and range. The primary outcome of interest will be a comparison of the mean change in GAD-7 scores at 3 months using the t-test. Secondary analysis will look at the comparison of mean change in GAD-7 longitudinally using repeated measures ANOVA. The repeated measures ANOVA will compare scores between groups and compare scores over time within groups. Similar analyses will be used for the other efficacy outcomes. The proportion of subjects with a visit, time to first visit, and number of visits will be compared using chi-square, log-rank, and Wilcoxon rank sum tests, respectively. A 5% significance level will be used for all tests.

Because there is minimal published data to guide power calculations in this population for our outcome of interest we have chosen a sample size of 12 for each interventional arm in this pilot study on the basis of feasibility as described by Julious [62]. This sample size of 12 will be increased to 20 per arm to account for an

[name]

estimated 40% drop out rate prior to completion of the MBSR intervention. Thus, the total number of subjects we expect to enroll to the intervention is 40. All subject data will be analyzed on an intention to treat basis.

9. Privacy/Confidentiality Issues

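### The secondary repeated measures ANOVA has no rule for missed visits and names no arm comparison at each visit; a mixed model with arm-by-visit contrasts would supply both

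*Combined protocol and SAP*

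**What the plan says.** Section 8 (Statistical Considerations) makes a t-test of GAD-7 change at 3 months the primary analysis. The secondary analysis is a "comparison of mean change in GAD-7 longitudinally using repeated measures ANOVA", described further only by: "The repeated measures ANOVA will compare scores between groups and compare scores over time within groups". The method is carried to other endpoints by "Similar analyses will be used for the other efficacy outcomes". The only statement on who is analysed is "All subject data will be analyzed on an intention to treat basis". Neither section says what happens to a subject who misses a visit.

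Section 5, under the Specific Aim 2 outcome assessments, names the primary outcome differently, as the "mean longitudinal change in GAD-7 scores between intervention groups at each time point".

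The protocol expects missed visits. Section 5 (Specific Aim 1, outcome 1d) says that, "assuming a 10% loss to follow up at each follow up time point", "we expect to have 65% who have completed all follow up evaluations". Section 8 separately sizes the study for 40% dropout before the MBSR course ends.

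On timing, section 5 says: "The standard MBSR course meets one day per week for 8 weeks". Follow-ups are at day 45 and months 3, 6 and 12.

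**The concern.** There are two gaps.

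**Missed visits.** Repeated measures ANOVA can be fitted classically, where a subject with one missing visit is dropped, or as a mixed model, where partial follow-up is kept. The plan does not choose. Under the classical fit the longitudinal estimates would describe only subjects who answered every survey. That sits badly with an intention-to-treat analysis of all subjects.

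**The contrast.** The two comparisons named for the ANOVA are not written as an arm difference at each visit. With change scores as the response, a between-group effect is an average over the four follow-ups. Tests over time within an arm do not compare arms. Some fall is also expected in both arms, because entry requires GAD-7 of at least 10. The reader of section 5 is promised the difference at each time point, and section 8 does not say which term of the model delivers it.

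The choice reaches beyond GAD-7. Table 2 schedules ten questionnaires at all five assessments, so up to nine others could inherit it. If the two mindfulness scales count as mechanism measures and not efficacy outcomes, the number is seven.

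**Working it through.** **Inputs from the documents.** 20 enrolled per arm and 40% dropout before course completion (section 8); four follow-ups, 10% loss at each, 65% completing all (section 5).

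**Assumed.** Equal SD at each visit; the same correlation r between any two GAD-7 scores, from 0.3 to 0.83 (the upper value equals the test-retest reliability quoted in section 5); dropout unrelated to outcome.

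**1. The plan's own figures.** 12/(1 - 0.40) = 20 per arm. 0.9^4 = 0.656, the stated 65%. Both reproduce.

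**2. Subjects and scores under a listwise fit.**
- Observed per arm under permanent dropout: 20 x 0.9^k = 18.0, 16.2, 14.6, 13.1.
- Subjects kept: 40 x 0.9^4 = 26.2.
- Permanent dropout: collected 2 x (18.0 + 16.2 + 14.6 + 13.1) = 123.8 scores; used 4 x 26.24 = 105.0; discarded 18.8 (15%).
- Independent misses (assumption): collected 40 x 4 x 0.9 = 144; used 105.0; discarded 39.0 (27%).

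**3. Precision at 10% per visit, permanent dropout.** Take 18, 16, 15 and 13 observed per arm. After baseline adjustment the correlation between visits is (r - r^2)/(1 - r^2) = r/(1 + r), so 0.23 to 0.45. The listwise variance of the arm difference is 2s^2/13 at every visit. The mixed-model variance is 2s^2 times the diagonal of the inverse of the summed information from each dropout pattern. At day 45 it is 2s^2/18, so the SE ratio is sqrt(18/13) = 1.18 whatever r is.

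| Increase in SE, listwise against mixed | Day 45 | Month 3 | Month 6 | Month 12 |
|---|---|---|---|---|
| Large-sample calculation | 18% | 11-12% | 8-10% | 1-4% |
| Simulation, 3,000 trials at each of r = 0.3, 0.5, 0.83 | 17-19% | 13-14% | 8-11% | 1-5% |

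In the simulation the unstructured REML model converged in 9,000 of 9,000 trials. The false-positive rate per visit contrast was 4.2-5.5% with Kenward-Roger degrees of freedom and 4.9-7.4% with a normal approximation.

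**4. The 40% dropout instead.** 20 x 0.6 = 12 per arm.
- If this loss falls between day 45 and month 3 (assumption), with 18, 12, 12, 12 observed: sqrt(18/12) = 1.22 at day 45, and 1.01-1.04 at later visits.
- If it all falls before day 45 and nobody leaves later (assumption), 12 are observed at every visit and the ratio is 1.

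**5. Day 45 and the course.** Session s falls 7(s - 1) days after session 1, so session 8 falls on day 49 of the course. Subjects enrol before session 1. With day 45 counted from the ED visit, as section 5 does for MACE, 45 < 49 and no MBSR subject can have finished. As an illustration, if the effect is D from month 3 on and fD at day 45, the average over visits is (f + 3)D/4. For f from 0 to 0.5 (assumption) that is 0.75D to 0.88D.

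**The case against.** The strongest reply is that every precision figure depends on a listwise fit that the plan never states. A repeated measures ANOVA is often run as a mixed model, and the commitment to analyse all subjects favours that reading. This stands. A reader might infer that the plan will discard partial data or breach intention to treat; the documents do not support that. They show an unspecified fit.

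A reader might also infer that the per-visit comparison is absent from the plan. It is not: section 5 names it, and comparing times within each group implies group-specific time effects. What is missing is the link between that comparison and the model in section 8. The dilution to 0.75D-0.88D matters only if an averaged effect is the sole result reported.

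The 10% figure is not the only attrition figure. Under the 40% dropout the listwise penalty can be larger at day 45 and close to nil afterwards, so a range is the fair statement. At month 3 the GAD-7 comparison is in any case protected by the separate t-test, which does not require all four visits.

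Finally, this is a secondary analysis in a 40-subject pilot. That limits the weight of the point. It does not remove the need to say in advance how partial follow-up is used.

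**Conclusion.** The point holds as a gap in specification with a cheap and better replacement. It should be fixed but is not critical.

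- If the ANOVA is fitted listwise, about 26 of 40 subjects remain and 15-27% of collected follow-up scores are set aside, depending on the pattern of misses.
- At 10% permanent loss per visit, the SE is larger by about 18% at day 45, 11-14% at month 3, 8-11% at month 6 and 1-5% at month 12. These figures rest on the assumed correlations of 0.3-0.83.
- If the 40% dropout falls between day 45 and month 3, the penalty is about 22% at day 45 and 1-4% later.
- If the ANOVA is fitted as a mixed model, there is no loss.

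Whatever the fit, section 8 does not tie the arm difference at each visit to a term in the model. An effect averaged over visits includes one taken before the course can be complete. Sections 5 and 8 also disagree on which comparison is primary and must be reconciled. It would be wrong to infer that the 3-month t-test is compromised; it does not depend on this choice.

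**What to change.** Replace the ANOVA in section 8 with a REML mixed model for change in GAD-7.

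- **Terms:** arm, visit, arm-by-visit and baseline GAD-7, using every subject with at least one follow-up score.
- **Covariance:** unstructured, with heterogeneous compound symmetry as the named fallback, and Kenward-Roger degrees of freedom.
- **Report:** the arm difference with 95% CI at each visit.
- **Status:** keep the 3-month comparison as the governing primary analysis, label the other visit contrasts exploratory, and align the outcome statement in section 5 with this.
- **Sensitivity:** the same model without the baseline covariate, because assignment is by enrolment period.
- **Other outcomes:** the same model for the other continuous efficacy scales.

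The cost is SAP wording and slightly more analysis in standard software; no new data are needed. The model assumes missing at random and does not remove confounding by enrolment period. Convergence was checked only at 18, 16, 15 and 13 per arm, which is one reason to name the fallback. Subjects with no follow-up score contribute no outcome and should be counted by arm: about 40 x 0.10 = 4 at 10% permanent loss per visit, and up to 40 x 0.40 = 16 if the 40% dropout precedes day 45.

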Specific Aim 1: To determine the feasibility of employing rapid cardiac risk stratification and psychological screening to identify patients with LRCP-A in the ED for subsequent referral to MBSR. Currently there are no tools regularly used in the ED to screen for LRCP-A, however, our *working hypothesis* is that evidence-based tools can be used to identify patients at risk for LRCP-A. To accomplish this, we will execute

[name]

a two-step prospective screening approach: 1. Determine score on the validated and widely used HEART scale [50, 51]. 2. Those with a HEART score <4 will complete the General Anxiety Disorder 7-item (GAD-7) questionnaire. Scores ≥ 10 are indicative of the criterion standard for moderate to severe symptoms of anxiety [52]. In this pilot study, feasibility will be assessed in a number of ways including the determination of the rate of eligible subjects per month, proportion of eligible subject who enroll, and proportion who complete the MBSR intervention. *Expected outcome:* This aim is designed to provide data regarding the feasibility of the risk stratification, psychological screening, and MBSR referral approach.

Specific Aim 2: To determine the effect of an MBSR training program for patients with LRCP-A on mental health (longitudinal GAD-7 scores, quality of life (PROMIS Global Short Form), and ED resource utilization (return ED visits). *Our working hypothesis* is that early referral to MBSR will help patients better regulate their thoughts, feelings, and bodily sensations related to their anxiety symptoms and have a significant positive effect on patient-centered outcomes such as mental health, quality of life as well as decreased ED resource utilization. To this end we will assign LRCP-A patients identified in SA1 to usual care referrals versus MBSR. We will then follow these patients for outcomes including change in GAD-7 scores, PROMIS Global Short Form, ED utilization among other outcomes at 6 weeks, 3 months, 6 months, and 1 year. *Impact:* This aim will establish a viable and novel treatment pathway for ED patients identified to be at risk for LRCP-A to ensure the possibility of early directed intervention.

3. Inclusion/Exclusion Criteria

Inclusion:

- Age: 18 through 70
- Chief complaint of chest pain
- HEART Score of 0-3 indicating Major Adverse Cardiac Events (MACE) risk equivalent to $\leq 2\%$
- GAD-7 score ≥ 10

Exclusion:

- Age <18 or ≥ 71
- Chief complaint of anxiety, panic, or similar

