- Prior personal ACS history (known at time of provider interview)
- Previous enrollment in the study
- Traumatic injury to the chest
- Suicidal ideation or active psychosis or behavioral issues requiring psychiatric monitoring
- Hemodynamic instability
- Non-English speaking
- Potential issues affecting follow up
 - Prisoners, homeless patients, out-of-town residences

4. Enrollment/Group Assignment

We will screen patients presenting to the Methodist ED with the chief complaint of chest pain. Sources for this information include the ED tracking systems and electronic medical records systems. Patients will be evaluated with the HEART score by their treating physician to determine if the patient initially qualifies to participate in the study. The treating physician will provide the information necessary to calculate the HEART score. Qualifying subjects will then be approached for final eligibility assessment using the GAD-7 and consented if interested and eligible.

Enrolled subjects will be assigned to either arm depending upon enrollment period. In the 8 weeks prior to the MBSR course commencement all subjects enrolled will be assigned to Arm 2: MBSR. This period will be immediately followed by 8 weeks of enrollment in Arm 1: Standard Referral. To decrease subject bias with regard to the interventional arm, potential enrollees will remain blinded to the enrollment period until informed consent is complete. This method of assignment has been chosen to help maximize intervention enrollment given the limited recruitment period.

5. Study Procedures (see figure 1 for an overview of protocol)

[figure not shown]
Figure 1 illustrates an overview of the flow of screening and enrollment for both specific aims. The patients who screen eligible in Aim 1 are the population of interest for assignment in Aim 2. The goal is to assign 40 subjects for the intervention arms. Each enrolled subject will have follow up evaluations at 45 days, 3 months, 6 months, and 1 year. Two ED physicians will independently review medical records of each enrolled patient for the described outcome variables and adjudicate any discordances by consensus.

Specific Aim 1: To determine the feasibility of employing rapid cardiac risk stratification and psychological screening to identify patients with LRCP-A in the ED for subsequent referral to MBSR.

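### Visit counts are compared without adjusting for prior use, although prior use is collected and the arms are filled in consecutive periods without randomisation

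*Combined protocol and SAP*

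**What the plan says.** - **Test.** Section 8 (Statistical Considerations) takes the proportion with a visit first and continues: "time to first visit, and number of visits will be compared using chi-square, log-rank, and Wilcoxon rank sum tests, respectively". It names no covariate, follow-up-time adjustment or effect estimate for visit counts. The sentence that extends the GAD-7 methods to the other efficacy outcomes refers to the t-test and repeated measures ANOVA, so it supplies no adjustment here. Section 8 also states: "A 5% significance level will be used for all tests".
- **Outcome.** Specific Aim 2 (Sections 2 and 5) names "ED resource utilization (return ED visits", in parentheses, as one of its outcomes.
- **Data.** Table 2 in Section 5 has a row beginning "Healthcare Utilization (12 mo Pre-ED" at the index visit and a row beginning "Healthcare Utilization (Post-ED assessment" at 45 days and 3, 6 and 12 months. Each has six custom items, whose content is not given.
- **Allocation.** Section 4: "Enrolled subjects will be assigned to either arm depending upon enrollment period". The MBSR arm is filled first over 8 weeks, and then "This period will be immediately followed by 8 weeks of enrollment in Arm 1: Standard Referral".

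**The concern.** In a randomised trial, an unadjusted rank test of counts is at least protected by chance balance. Here the arms are recruited in different weeks, and the plan has no other safeguard against one arm holding more frequent attenders. Section 1 describes patients who keep returning for care despite reassurance, so lasting differences between patients in visit frequency are plausible. Any such difference between arms would be read as an effect of MBSR on utilisation, in either direction.

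The plan analyses GAD-7 as change from baseline but makes no use of the baseline for utilisation. The Wilcoxon test also yields no rate ratio, which is what a pilot should hand to the next trial. It takes no account of how long each subject was observed.

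**Working it through.** **The plan's own figure.** Section 8 gives no power or effect size for visits. Its sample size reproduces: 12 / (1 − 0.40) = 20 per arm, 40 in total.

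**Assumed inputs.** The documents give no visit rate, dispersion or prior/later correlation. The simulations assume a mean of 1.5 visits per year and gamma between-subject variation with dispersion 0.5 or 1.0, each subject keeping the same underlying rate before and after. Tests are two-sided at 5%; the plan states the level but not the sides. The adjusted model is quasi-Poisson with a t reference and log(prior count + 0.5) as covariate. Settings used 800 to 4,000 simulated trials.

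**Step 1: false positives, 20 per arm, no treatment effect.**

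| Underlying use, Arm 2 relative to Arm 1 | Dispersion | Wilcoxon | Adjusted quasi-Poisson |
|---|---|---|---|
| 1 (no imbalance) | 0.5 and 1.0 | about 5% | 4% to 5% |
| 1.5 | 0.5 | about 20% | 10% to 11% |
| 1.5 | 1.0 | about 14% | about 8% |
| 0.67 | 0.5 | 15% | 9% |
| 0.67 | 1.0 | 13% | 8% |

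The 0.67 rows are the direction that would flatter MBSR.

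Rank ANCOVA on prior count agrees. With an assumed mean of 2 visits, gamma shape 1 or 3 and a use ratio of 0.67, rejections fall from 13% to 7% and from 22% to 14% at 20 per arm. At 12 per arm they fall from 9% to 6% and from 14% to 10%.

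**Step 2: bias that remains.** In one run with the ratio at 1.5, the mean log rate ratio was 0.42 unadjusted (ln 1.5 = 0.41) and 0.16 adjusted. Since exp(0.16) = 1.17, a spurious 17% increase remained. A single noisy 12-month count only partly captures a subject's underlying rate.

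**Step 3: precision.** For a linear comparison with one covariate, variance ratio (adjusted/unadjusted) = (1 − ρ²)(N − 3)/(N − 4), where ρ is the prior/later correlation.
- N = 40: ρ = 0.2 gives 0.96 × 37/36 = 0.99; ρ = 0.3 gives 0.94; ρ = 0.5 gives 0.77; ρ = 0.7 gives 0.52.
- N = 24: 1.01, 0.96, 0.79 and 0.54.
- Break-even ρ = √(1/(N − 3)): √(1/37) = 0.16 at N = 40 and √(1/21) = 0.22 at N = 24.

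In the simulations with fully stable use, the SD of the log rate ratio fell from 0.351 to 0.321 (1 − 0.321/0.351 = 9%) at dispersion 0.5 and from 0.408 to 0.338 (17%) at dispersion 1.0. Repeat runs gave 6% and 19%. When only 40% of subjects kept their underlying rate, nothing was gained: 0.359 to 0.364, and 0.430 to 0.426.

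**Step 4: power for a halved rate, split by cause.** At dispersion 0.5: Wilcoxon 35%, unadjusted quasi-Poisson 40%, adjusted 43%. At dispersion 1.0: 27%, 29% and 38%. So the covariate itself adds 3 and 9 points; the rest comes from changing the model.

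**Step 5: choice of variance.** With no effect and no imbalance, quasi-Poisson with a t reference rejects in 4% to 5%. Robust Poisson with an uncorrected sandwich variance and a normal reference rejects in about 7% to 9% at 20 per arm and 8% to 11% at 12 per arm.

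**Step 6: observation time.** Section 8 allows 40% dropout before MBSR is completed; Section 5 expects 10% loss at each follow-up. If counts come from the follow-up surveys, and loss is assumed to be 40% in one arm and 10% in the other, the Wilcoxon test on raw counts rejects a true null in 10% to 12% of trials, and a model with an offset in about 5%. If counts come wholly from the record review in Section 5, this matters less. The plan does not say which source is used.

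**The case against.** The Wilcoxon test is a valid, robust choice for skewed counts. It holds its level when the arms are alike, and Section 8 also reports group means, SDs and ranges. Visits are not the primary outcome, the trial is a pilot ("we have chosen a sample size of 12 for each interventional arm in this pilot study on the basis of feasibility"), and even the adjusted model has only about 38% to 46% power for a halved rate. The visit in Section 8 is undefined: item 1e of the Aim 1 outcomes in Section 5 concerns PCP or mental-health visits, for which prior ED use is not the matching baseline. Nor is it shown that the pre- and post-ED items count the same thing.

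All of this stands, and it limits the weight of the point. It does not answer the core of it: the arms are not randomised, a likely predictor is already collected, and the comparison ignores it.

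A reader might infer three stronger claims that the documents do not support:
- **That the plan wastes precision.** This needs a prior/later correlation above about 0.16 to 0.22, and the gain is small below 0.3. No correlation is given.
- **That adjustment would cure the confounding.** Arm and enrolment period coincide completely, so a period effect not carried by prior use cannot be separated from treatment.
- **That the analysis favours MBSR.** The direction of any imbalance is unknown.

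**Conclusion.** The point holds as one about bias in a secondary outcome. A difference in prior use between consecutively enrolled arms enters the visit comparison uncorrected. Under the assumed inputs (20 per arm, mean 1.5 visits per year, fully stable variation, dispersion 0.5 to 1.0), a 1.5-fold imbalance gives false positives in about 14% to 20% of trials, falling to about 8% to 11% after adjustment. These sizes depend on the assumptions, and full stability is the case most favourable to adjustment.

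Precision is a possible extra benefit: the SE falls by roughly 10% to 20% (6% to 19% across runs) if use is stable, and by almost nothing if it is not. Neither the sample size nor the primary GAD-7 analysis is affected. Non-random allocation remains the underlying limitation, which no covariate removes.

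**What to change.** In Section 8, for return ED visits:
1. State that the visit counted here is a return ED visit. Confirm that the pre- and post-ED custom items both count these. Name the source of the counts (survey or record review).
2. Prespecify a quasi-Poisson model with a t reference distribution: arm, log(prior 12-month ED count + 0.5), and log days observed as offset. Do not use robust Poisson without a small-sample correction.
3. Report the rate ratio with its 95% CI, and keep the Wilcoxon test as a sensitivity analysis. Rank ANCOVA on prior count is an acceptable simpler form, though it gives no rate ratio and, on raw counts, does not handle unequal observation time.
4. State that adjustment reduces but does not remove bias, and cannot correct for enrolment period.

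The cost is SAP wording and a few lines of code. If the items in Table 2 do count ED visits, no new data are needed. The downside is some reliance on a model and on prior counts that are presumably self-reported. Fixing the model before outcome data are seen also prevents a later choice between adjusted and unadjusted results.
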